4.3.1. Background and Demographic Characteristics

Descriptive statistics will be used to summarize demographic characteristics (age, gender, Fitzpatrick skin type, and race) and background characteristics for the randomized subject population. Past/coexistent medical history information for all randomized subjects will be presented in a by-subject listing.

4.3.2. Study Product/Visit Compliance

Descriptive statistics will be used to summarize study product compliance for the randomized subject population.

4.4. **Prior and Concomitant Medications**

Prior and concomitant medication information for all randomized subjects will be presented in a by-subject listing.

4.5. Efficacy Evaluation

This section is not applicable to this study.

4.6. Safety Evaluation

4.6.1. Local Tolerability Assessment

All assigned scores during the study for subjects who complete the study will be summarized using frequency counts by treatment for Days 2, 3 and 4. Selected pairwise comparisons will be performed on the mean of the Day 3 and Day 4 response scores (sum of erythema and edema

scores) in the context of the analyses of variance (ANOVA). Pairs to be compared are: each study product irradiated versus non-irradiated and all pairwise comparisons on each side (CCP-020 [Diacerein 1%] topical ointment versus vehicle ointment on both the irradiated and non-irradiated sides and CCP-020 [Diacerein 1%] topical ointment versus untreated and vehicle ointment versus untreated on the irradiated side).

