3. INVESTIGATIONAL PLAN

3.1. Study Design

This is a single-center, randomized, within-subject comparison study of CCP-020 (Diacerein 1%) Topical Ointment and vehicle ointment. CCP-020 (Diacerein 1%) Topical Ointment and vehicle ointment will each be applied to 2 sites, one which will be irradiated and one which will remain non-irradiated. The irradiated and non-irradiated sites will be compared with each other and with an untreated irradiated control.

A total of 4 application sites (2 cm x 2 cm each) will be marked on the subject's lower thoracic area of the back: 2 sites on each side of the back – 2 sites for CCP-020 (Diacerein 1%) Topical Ointment and 2 sites for vehicle ointment. Each study product will be applied according to the randomization scheme in an amount of 0.2 mL under occlusive patch conditions once during the study.

Approximately 24 (\pm 2) hours post study product application, the patches will be removed by study staff. The sites will then be graded for cutaneous reactions by a trained evaluator and the designated sites, including the untreated site, will be exposed to irradiation. One side of the back will be designated for irradiation and the other side will remain non-irradiated. An additional site will be marked on the "irradiated side" of the back which will receive no treatment, but will receive irradiation to serve as an untreated irradiated control. The sites and control will be examined at approximately 24 and 48 hours post irradiation and graded for reactions. Cutaneous reactions at the application sites will be evaluated using a visual scale that rates the degree of erythema, edema, and other signs of cutaneous irritation (see Table 3 and Table 4).

Safety evaluations include collection of adverse events (AEs).

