3.4. Treatments

3.4.1. Investigational Products and Control

Investigational Product(s):

CCP-020 Topical Ointment

CCP-020 is a topical ointment, 1% (w/w). All excipients used in the topical formulation meet United States Pharmacopeia (USP)/ National Formulary (NF) criteria and are commonly used in

The CCP-020 topical ointment and vehicle ointment will be applied topically, under occlusive patch conditions once over a 4-day period. Each product will be applied to 2 sites (one irradiated site and one non-irradiated site) on the lower thoracic area of each subject's back for approximately 24 (+/- 2) hours. An amount of investigational product sufficient to cover an area of the back approximately 2 cm x 2 cm will be applied (approximately 0.2 mL).

CCP-020 topical ointment and vehicle ointment should be stored at room temperature (15°C/59°F to 30°C/86°F). The PI will be responsible for the suitable storage of the IPs in compliance with the storage instructions and must restrict access to the investigative personnel only.

Lot numbers will be given in the clinical study report.

Manufacturer:

TWi Pharmaceuticals will be responsible for the manufacturing and filling into the primary package; aluminum tubes. TWi Pharmaceuticals will be responsible to package and distribute to TKL. CCP will be responsible for final release of the product. TKL will be responsible for labeling the product upon site delivery.

Control

An untreated irradiated non-occlusive (open) 2 cm x 2 cm site will serve as a control.

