3.4.5. Assignment to Treatment

3.4.5.1. Randomization

Each subject who signs an informed consent and successfully completes the screening procedures will be enrolled in the study. Upon enrollment, each subject will be assigned a unique number, which will correspond to the subject number on the randomization code indicating application placement of the study materials. Each subject in this study will serve as his or her own control.

For each subject, one side of the back will be designated for irradiated sites and the other side will be for non-irradiated sites. On each side one application site will be assigned to the CCP-020 [Diacerein 1%] topical ointment and one will be assigned to the vehicle ointment according to the randomization schedule. On the irradiated side only one additional site will be assigned to the untreated irradiated control.

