3.4.5.2. Blinding

Investigative personnel who are involved in the preparation/application and removal of the treatments (CCP-020 [Diacerein 1%] topical ointment and vehicle ointment) will be unblinded and will not perform the evaluation of skin responses. The trained evaluator who will be evaluating skin responses will be blinded to IPs and the treatment allocation; however, because of the demarcations/skin coloration remaining on the skin following patch removal, complete blinding of the evaluators cannot be completely assured.

Investigative personnel, including the Investigator and the trained evaluator involved in the evaluation of responses, will remain blinded during the course of the study until Database Lock and finalization of the Statistical Analysis Plan (SAP).

In the event of an emergency, if possible, the Investigator or designee will contact the Sponsor with notification of the intent to unblind the treatment codes prior to the actual unblinding. If it is not possible to notify the Sponsor prior to the unblinding, the Investigator or designee will contact the Sponsor immediately following the unblinding procedure and follow with a written notification to document the exact manner in which the code was broken and the justification for the unblinding. The Investigator will communicate the treatment identification to only the investigative personnel who require the information to manage the emergency. Unblinding will happen on site at TKL.

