On Day 4, approximately 48 (\pm 4) hours after irradiation (ie, approximately 72 (\pm 4) hours following product application), all application sites and the untreated control site will be evaluated. Adverse events and concomitant medications will be reviewed and recorded, as appropriate. A UPT will be performed for female subjects of childbearing potential.

Retest

Although not all observations of erythema and edema are associated with phototoxicity, erythema and edema must be observed for a reaction to be suspected of being a positive phototoxic reaction. An increase in the intensity of the reaction over time further supports an assessment of phototoxicity. If a reaction is observed at both the irradiated and non-irradiated product sites (ie, if contact sensitization or irritation may have occurred), the reaction upon retest must be at least one grade more intense at the irradiated site than at the non-irradiated site for the reaction to be suspected of being a phototoxicity reaction (refer to Section 3.5.7 for response grades and notations).

If it is determined by the Investigator that a retest should be performed, then the retest patches will be applied as soon as the original reactions have resolved. The Investigator will determine the patch conditions to use during the Retest (see Section 3.4.3). The study material will be applied to naive sites on the back, using appropriate patches to further discriminate a phototoxic reaction from an irritation reaction. Identical patches will be applied to sites previously unexposed to the study material. Approximately 24 (\pm 2) hours later one site will be irradiated with 16 J/cm² of UVA followed by ½ MED of UVB radiation using a filtered light source. An additional untreated site will be irradiated with 16 J/cm² of UVA followed by ½ MED of UVB radiation using a filtered light source. An

be evaluated upon patch removal and approximately 24, 48, and 72 hours after irradiation. Concomitant medications and AEs will also be reviewed.

In some cases the retest may be done on the individual ingredients of the products.

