4. STATISTICAL METHODS

4.1. General Considerations for Data Analysis

The focus of the statistical analysis will be the comparison with controls of the phototoxic response to the study products. The parameter for phototoxicity will be the mean of Day 3 and 4 scores (sum of erythema and edema).

All statistical processing will be performed using the SAS[®] system (version 9.2 or higher). No interim or subgroup analyses are planned.

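### Do the six site comparisons in Section 4.6.1 need a named subject term and error term before they can be relied on?

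*Combined protocol and SAP*

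**What the plan says.** Section 4.1 sets the aim: "The focus of the statistical analysis will be the comparison with controls of the phototoxic response to the study products". The variable is the mean of the Day 3 and Day 4 scores, each the sum of erythema and edema.

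Section 4.6.1 analyses it "in the context of the analyses of variance (ANOVA" and lists the contrasts: "Pairs to be compared are: each study product irradiated versus non-irradiated and all pairwise comparisons on each side". Written out, there are six:

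- irradiated versus non-irradiated, for CCP-020 and for vehicle (2)
- CCP-020, vehicle and untreated against each other on the irradiated side (3)
- CCP-020 versus vehicle on the non-irradiated side (1)

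The synopsis repeats this. Sections 4.1, 4.2 and 4.9 add no model term, covariance, degrees of freedom or alpha.

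The design sections say more. Section 3.1: "This is a single-center, randomized, within-subject comparison study". Section 3.4.5.1: "Each subject in this study will serve as his or her own control". Section 3.4.5.2 keeps the evaluating personnel blinded "until Database Lock and finalization of the Statistical Analysis Plan (SAP".

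**The concern.** All five scores come from one person, so the standard error of a difference depends on how the model treats the subject and on which sites contribute to the residual. The text fits several models: one ANOVA over five sites, or separate ANOVAs for each side, with a further model for the two pairs that span both sides. A residual shared by several pairs is right for each of them only if the pairwise differences have equal variance.

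There are reasons to doubt that here. Scores cannot fall below 0, and sites that seldom react vary little. One side is irradiated and the other is not. The control differs from the occluded product sites: "An untreated irradiated non-occlusive (open) 2 cm x 2 cm site will serve as a control". If variances differ, a pooled residual can be too small for the irradiated-side pairs and too large for the non-irradiated pair. These six comparisons are the only inferential analysis planned, so p-values that depend on an unstated choice deserve a check.

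**Working it through.** **Inputs.** From the documents: five sites per subject, six pairs, 30 completers, scores floored at 0. Assumed, because the documents do not give them: a two-sided 5% level; variance 1 at irradiated sites and k at non-irradiated sites; correlation r between sites on the same side, and r or r/2 across sides. The plan has no figure of its own to reproduce, since Section 4.2 justifies 30 subjects by convention.

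**Formula.** With a subject block over m sites and site covariance matrix S, E[MSE] = (trace S − sum S / m)/(m − 1). The ratio of assumed to true variance of a difference is 2·E[MSE]/Var(difference). The large-sample size is 2·(1 − Φ(1.96·√ratio)).

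**Case 1, k = 1, common r.** E[MSE] = 1 − r and Var(difference) = 2(1 − r). The ratio is 1 and the size is 5.0% for all six pairs, at any r.

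**Case 2, k = 0.5, r = 0.** trace = sum = 4, so E[MSE] = (4 − 0.8)/4 = 0.8.

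- Irradiated pair: 2 × 0.8/2 = 0.80, size 8.0%.
- Irradiated versus non-irradiated: 1.6/1.5 = 1.07, size 4.3%.
- Non-irradiated pair: 1.6/1.0 = 1.60, size 1.3%.

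At r = 0.8 these become 6.3%, 5.2% and 0.8%.

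**Case 3, k = 1, r = 0.8 within side and 0.4 across.** trace = 5 and sum = 5 + 4.8 + 1.6 + 4.8 = 16.2, so E[MSE] = (5 − 3.24)/4 = 0.44.

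- Same-side pairs: 0.88/0.4 = 2.2, size 0.4%.
- Irradiated versus non-irradiated: 0.88/1.2 = 0.73, size 9.3%.

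The direction of error for the irradiated pairs reverses between Cases 2 and 3.

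**Per-side ANOVA with subject.** Same-side pairs stay at 5.0% at every k and r, unless the open site is also given a different variance. With half the variance there and r from 0 to 0.8, irradiated CCP-020 versus vehicle is 7.4 to 5.6% and product versus untreated 3.9 to 4.7%.

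**Subject omitted, k = 1, r = 0.5.** The ratio is 2.0 and the size is 0.6%. This reading sets aside the design statements in Sections 3.1 and 3.4.5.1.

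**One invented data set, 30 subjects.** The listed subjects score 1 and all others 0. Irradiated CCP-020: 1–9. Irradiated vehicle: 1–3 and 10. Untreated: 1, 2, 11. Non-irradiated CCP-020: 1, 2, 4, 12. Non-irradiated vehicle: none. For irradiated CCP-020 versus vehicle the difference is (9 − 4)/30 = 0.167, with SE = √(2·MSE/30).

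| Model | MSE | df | SE | t | p |
|---|---|---|---|---|---|
| Five sites, subject | 9.00/116 = 0.0776 | 116 | 0.0719 | 2.32 | 0.022 |
| Irradiated side, subject | 5.311/58 = 0.0916 | 58 | 0.0781 | 2.13 | 0.037 |
| Own pair (paired t) | 3.083/29 = 0.1063 | 29 | 0.0842 | 1.98 | 0.057 |
| Five sites, no subject | 15.933/145 = 0.1099 | 145 | 0.0856 | 1.95 | 0.053 |

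For non-irradiated CCP-020 versus vehicle (4/30 = 0.133), the order partly reverses: p = 0.066 with five sites and subject, 0.043 per side (the same as paired), and 0.12 with no subject.

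**Cost of pair-specific tests.** Critical t is 2.045 on 29 df against 1.981 on 116 df, about 3% larger. The simulation used scores of 0, 1 or 2 with a quarter of reactors at 2, day-to-day latent correlation 0.8 and r = 0.5. With 30% reacting at irradiated CCP-020 and 10% elsewhere, power for CCP-020 versus vehicle is 69% paired and 79% five-site. With half the correlation across sides, power for irradiated versus non-irradiated CCP-020 is 59% and 73%. The reverse holds for a non-irradiated difference (20–25% against 3–5% reacting, irradiated sites 30–40%): about 60–90% paired and 33–76% five-site.

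**The case for a change.** The strongest case for a change is that the within-subject wording settles only the block. Among subject-blocked models alone the p-values above run from 0.022 to 0.057. In a second invented set, where three subjects score 1 at irradiated CCP-020 and everything else is 0, they run from 0.005 (five-site) through 0.032 (per side) to 0.083 (paired). No reading is conservative for every pair, unequal variances are plausible with floored scores, and a sentence written before unblinding would rule out a choice made on the data. Part of the power advantage of the pooled test also comes from its running above 5% for the irradiated pairs.

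All of that stands as arithmetic. It does not show that the planned analysis is wrong. The spread comes from constructed scores, and the documents neither establish nor exclude the variance pattern behind it. Stating the block and residual only writes down what the analyst must specify in the SAP anyway. Requiring six paired tests goes further: it replaces one defensible error term with another, gains on the non-irradiated pair and loses on the irradiated pairs. With sparse scores the paired test is itself off nominal, at 1.2 to 4.2% for the non-irradiated pair in simulation.

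**Conclusion.** This is missing detail that analysts fill sensibly, and no change to the plan follows. The design statements point to a subject-blocked ANOVA, and the SAP still to be finalized is the natural place to record the residual. Any error is bounded by assumption only. It is nil with equal variances and a common correlation. In the closed-form cases worked above, the five-site residual gives about 0.4% to 9.3% against a 5% level that the plan never states.

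The consequences are limited to group-level p-values and intervals. Section 3.5.1 rests a suspected phototoxic reaction on observed erythema and edema and, where both product sites react, requires that "the reaction upon retest must be at least one grade more intense at the irradiated site than at the non-irradiated site". Section 3.5.7.1 requires a reproducible result on retest before phototoxicity is inferred, and Section 4.6.1 also reports frequency counts by treatment. None of these depends on the error term.

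The conclusion would be weaker if a declared alpha or pass/fail rule were attached to these p-values, or if the subject effect were left out of the model. The documents contain no such rule, and their design statements argue against leaving the subject out.

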4.6.2. Adverse Events

Adverse events will be summarized as an overall incidence of at least one event, incidence within body systems only, incidence by body system and preferred term, and by highest severity. Each subject will contribute only once (e.g., the first occurrence) to each of the rates, regardless of the number of occurrences (events) the subject experiences.

Treatment-emergent AEs will be summarized and tabulated by the system organ class and preferred term, by severity (mild, moderate, severe) and by relationship to study product (not related, unlikely, possible, probable, and definite).

Treatment-emergent will be defined as any AE with an onset date on or after the first study product administration date. Any event with a missing onset date will be included as a treatment-emergent AE.

Deaths and SAEs will be listed by subject.

4.7. Other topics

There are no other topics being evaluated.

4.8. Interim analyses

No interim analyses are anticipated.

4.9. Special Methods

This section is not applicable for this protocol.

5. **ADMINISTRATIVE PROCEDURES**

5.1. Ethics and Good Clinical Practice

This study must be carried out in compliance with the protocol and in accordance with TKL Research, Inc.'s standard operating procedures. These are designed to ensure adherence to Good Clinical Practices guidelines, as described in:

- ICH Harmonized Tripartite Guidelines for Good Clinical Practice 1996. Directive 91/507/EEC, The Rules Governing Medicinal Products in the European Community.
- United States (US) 21 Code of Federal Regulations (CFRs) dealing with clinical studies (including parts 50 and 56 concerning informed consent and IRB/IEC/EEC regulations).
- Declaration of Helsinki, concerning medical research in humans (Recommendations Guiding Physicians in Biomedical Research Involving Human Subjects, Helsinki 1964 and amendments).

The PI agrees, when signing the protocol, to adhere to the instructions and procedures described in it and thereby to adhere to the principles of GCP that it conforms to.

5.2. Institutional Review Board

Before implementing this study, the protocol, the ICF and other information to subjects, must be reviewed by a properly constituted IRB. A signed and dated statement that the protocol and informed consent have been approved by the IRB must be given to Sponsor before study initiation. This committee must also approve any amendments to the protocol, other than administrative ones, and a signed and dated statement of approval must be sent to the Sponsor prior to initiation of the amendment procedures. The name and occupation of the chairman and the members of the IRB must also be supplied to Sponsor.

5.3. Informed consent

The Investigator must explain to each subject (or legally authorized representative) the nature of the study, its purpose, the procedures involved, the expected duration, the potential risks and benefits involved, and any discomfort it may entail. Each subject must be informed that participation in the study is voluntary, that he/she may withdraw from the study at any time, and that withdrawal of consent will not affect his/her subsequent medical treatment or relationship with the treating physician.

This informed consent should be given by means of a standard written statement, written in nontechnical language. The subject should read and consider the statement before signing and dating it, and he/she should be given a copy of the signed document. No subject can enter the study before informed consent has been obtained from him/her, or his/her legally authorized representative. The ICF is considered to be part of the protocol, and must be submitted by the PI with it for IRB approval. Any changes to the proposed ICF suggested by the PI must be agreed to by Castle Creek Pharmaceuticals, LLC before submission to the IRB and a copy of the approved version must be provided to Castle Creek Pharmaceuticals, LLC after IRB approval.

5.4. Declaration of Helsinki

The PI must conduct the study in accordance with the laws and regulations of the country in which the study is conducted, as outlined in the Declaration of Helsinki.

5.5. Changes in Planned Study Conduct

5.5.1. Protocol amendments

With the exception of changes in the visit schedule and/or administrative changes, any changes or additions to this clinical study protocol require a written protocol amendment that must be approved by Castle Creek Pharmaceuticals, LLC and the PI before implementation. Amendments significantly affecting the safety of subjects, the scope of the investigation or the scientific quality of the study, require additional approval by the appropriate IRB. A copy of the written approval of the IRB, which becomes part of the protocol, must be given to Castle Creek Pharmaceuticals, LLC. Examples of amendments requiring such approval are:

- 1. an increase in study product dosage or duration of product exposure of subjects,
- 2. a significant change in the study design (e.g., addition or deletion of a control group),
- 3. an increase in the number of invasive procedures to which subjects are exposed, and
- 4. addition or deletion of a test procedure for safety monitoring.

These requirements for approval should in no way prevent any immediate action from being taken by the Investigator or the Sponsor in the interests of preserving the safety of all subjects included in the study. If an immediate change to the protocol is felt to be necessary by the Investigator and is implemented by him/her for safety reasons the study Sponsor should be notified and the IRB should be informed within 10 working days.

Amendments affecting only administrative aspects of the study do not require formal protocol amendments or IRB approval, but the IRB must be kept informed of such administrative changes. Examples of administrative changes not requiring formal protocol amendments and IRB approval that can be treated as administrative amendments include:

- 1. changes in the staff used to monitor studies, and
- 2. minor changes in the packaging or labeling of the study product.

